8.2 Baseline Definitions

The study baseline will be defined as the last available, non-missing observation prior to first study drug (emricasan or placebo) administration, unless specifically mentioned otherwise.

For survival models: The first valid MBT test will be defined as the baseline and day 0 of follow up. For MELD scores, the first value measured on or after the day of the first valid MBT will serve as baseline value, even if there are later MELD results available prior to first study drug (emricasan or placebo) administration. The MELD progression outcome, 4 point increase in MELD, will thus be calculated by comparing each MELD score to the first available MELD score on or after the first valid MBT date.

Exalenz Bioscience Ltd.	Last update: August 8, 2019
SAP for Protocol CON-EX-0217: Companion protocol for the ¹³C-Methacetin Breath Test using the BreathID® MCS System for Conatus phase 2 study of Emricasan, an Oral Caspase Inhibitor, under protocol IDN-6556-17 (IND111463)	Document Version: 1.0
Document N°: CSD00109	Page 12 of 21

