8.4.1 Primary Endpoint

The MBT parameter used to predict hepatic decompensation event is PDR_{peak}. Any PDR_{peak} value of less or equal to 5.5 %/h (see **Appendix A** for detailed description of parameter calculation) will be considered as ‘high risk’ and any value above that threshold will be considered as ‘lesser risk’. The dichotomous MBT result will be tested for significance using the Cox proportional hazards regression model with site and Conatus protocol IDN-6556-17 randomized arm as covariates. If the Conatus protocol IDN-6556-17 randomized arm factor is found non-significant (i.e. p-value > 0.05), then this factor will not be a covariate for the main analysis to be performed. If the Conatus protocol IDN-6556-17 randomized arm factor is found statistically significant (i.e. p-value ≤ 0.05), then the main analysis will be performed keeping this factor as a covariate (to ‘adjust’ the analysis for treatment).

The following list defines the hepatic decompensation events for the primary endpoint:

- Liver-specific mortality
- Liver transplant
- New and/or recurrent hepatic decompensation events

Exalenz Bioscience Ltd.	Last update: August 8, 2019
SAP for Protocol CON-EX-0217: Companion protocol for the ¹³C-Methacetin Breath Test using the BreathID® MCS System for Conatus phase 2 study of Emricasan, an Oral Caspase Inhibitor, under protocol IDN-6556-17 (IND111463)	Document Version: 1.0
Document N°: CSD00109	Page 13 of 21

- Variceal hemorrhage that required ‘non-drug therapy’ (e.g. variceal ligation, sclerotherapy) based on the AE log or requiring hospitalization
- Portal hypertensive gastropathy hemorrhage requiring hospitalization
- Occurrence of large gastroesophageal varices or any varices with red wale sign (classified as severe in the AE log) and that required ‘non-drug therapy’ (e.g. variceal ligation or sclerotherapy) based on the AE log to avoid hemorrhage
- Ascites requiring diuretics (in a subject without prior history of ascites requiring diuretics) or refractory ascites requiring ‘non-drug therapy’ (e.g. paracentesis) based on the AE log (in a subject with history of ascites requiring diuretics).
- Any onset of hepatic encephalopathy (HE) requiring hospitalization (classified as SAE) in the absence of known co-morbidities or alternative causes.
- Hepatorenal syndrome requiring hospitalization
- Spontaneous bacterial peritonitis (SBP) requiring hospitalization
- MELD score progression defined as any increase ≥ 4 points from baseline

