These hepatic decompensation events are identified using the study’s ‘new decompensation event’ dataset as well as events listed in the AE and SAE logs, the reason for (early) termination, the comment and the lab results (incl. MELD scores) datasets. All potential hepatic decompensation events will be adjudicated through a medical review prior to the primary efficacy analysis and blinded to the breath test results. Once defined and adjudicated, the first of the hepatic decompensation events after the first valid MBT will be used for the respective event-free survival analysis.

All MELD scores will be calculated using the formula from the US Organ Procurement and Transplantation Network (OPTN) Policy from 2016 (**Appendix B**). MELD score progression will not include subjects who are started on anticoagulants after the first valid

Exalenz Bioscience Ltd.	Last update: August 8, 2019
SAP for Protocol CON-EX-0217: Companion protocol for the ¹³C-Methacetin Breath Test using the BreathID® MCS System for Conatus phase 2 study of Emricasan, an Oral Caspase Inhibitor, under protocol IDN-6556-17 (IND111463)	Document Version: 1.0
Document N°: CSD00109	Page 14 of 21

MBT (and prior to the identified MELD progression event) that can affect the PT or INR at the time of MELD assessment.

The time-to-first event will be derived as the number of days between the day of the screening MBT test and the date when the first hepatic decompensation event occurs or when a subject is censored (i.e., event/censored date minus screening MBT date plus 1). Subjects will be censored at their last study visit for the following reasons:

- If a subject discontinues the study prior to the end of the study without experiencing a hepatic decompensation event
- If a subject reaches the Final Treatment visit without experiencing a hepatic decompensation event
- If a subject develops hepatocellular carcinoma (HCC)

Survival analysis will be conducted using the Cox proportional hazard model. The model summary will include the number of subjects in the model, and a table with each covariate in a separate line specifying the coefficient's value, Hazard Ratio, Hazard Ratio 95% Confidence Interval and p-value. In addition, a Kaplan-Meier plot for event-free survival will be presented, stratified by MBT parameter along with the MBT parameter log-rank p-value. Additionally a crosstab table of MBT parameter and events will be presented.

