APPENDIX B – MELD SCORE FORMULA FROM US OPTN POLICY (2016)

Subjects receive an initial MELD(i) score equal to:

$$\text{initial MELD(i)} = 0.957 \times \text{Loge(creatinine mg/dL)} + 0.378 \times \text{Loge(bilirubin mg/dL)} + 1.120 \times \text{Loge (INR)} + 0.643$$

Laboratory values less than 1.0 will be set to 1.0 when calculating a subject's MELD score.

The following subjects will receive a creatinine value of 4.0 mg/dL:

- Subjects with a creatinine value greater than 4.0 mg/dL
- Subjects who received two or more dialysis treatments within the prior 7 days
- Subjects who received 24 hours of continuous veno-venous hemodialysis (CVVHD) within the prior 7 days

The MELD score derived from this calculation will be rounded to the tenth decimal place and then multiplied by 10. The maximum MELD score is 40.

For candidates with an initial MELD score greater than 11, the MELD score is then recalculated as follows:

$$\text{MELD} = \text{MELD(i)} + 1.32 * (137 - \text{Na}) - [0.033 * \text{MELD(i)} * (137 - \text{Na})]$$

Sodium values less than 125 mmol/L will be set to 125, and values greater than 137 mmol/L will be set to 137.

Resources:

https://optn.transplant.hrsa.gov/media/1200/optn_policies.pdf Section 9.1.D on Page 169

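### The anticoagulant rule for MELD progression discards rises that INR did not cause in subjects who start the drug after the first valid MBT, and does not reach subjects already taking one

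*SAP*

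**What the plan says.** SAP 8.4.1 lists among the primary events "MELD score progression defined as any increase ≥ 4 points from baseline". No confirmatory value is asked for. Under SAP 8.2, for the MELD baseline "the first value measured on or after the day of the first valid MBT will serve as baseline value".

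The only anticoagulant rule is in SAP 8.4.1. Its sentence runs over a page break: "MELD score progression will not include subjects who are started on anticoagulants after the first valid", continuing "MBT (and prior to the identified MELD progression event) that can affect the PT or INR at the time of MELD assessment". It therefore has two limits: the start must come before the MELD rise, and the drug must be able to affect PT or INR when MELD is assessed.

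Three neighbouring provisions matter:

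- All potential events go to a medical review blinded to the breath test (SAP 8.4.1). No criterion is given for INR change on an anticoagulant.
- The censoring reasons in SAP 8.4.1 are discontinuation, reaching the Final Treatment visit, and HCC. Starting an anticoagulant is not among them.
- Exploratory analyses 13 and 14 in SAP 8.4.3.1 take MELD progression alone, and the primary composite without it.

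Eligibility for anticoagulated subjects is set by the main emricasan protocol, which is not supplied.

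**The concern.** The rule exists because an anticoagulant raises INR without any change in the liver, and INR is a term in MELD. Neither of its limits asks whether INR produced the rise, so the rule misses its target in two ways.

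- **New starters.** Once the drug is started, every later MELD progression is disqualified, including one driven wholly by creatinine, bilirubin or sodium. As the start is not a censoring reason, the subject goes on contributing event-free follow-up for a component that can no longer be met.
- **Prior users.** A subject already on the drug at the first valid MBT is outside the rule. A large INR change can then reach the threshold through drug effect alone, and the reviewers have no written basis for handling it.

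At stake is the accuracy of one component of the primary endpoint against which the PDR peak cut-off of 5.5 %/h is to be validated.

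**Working it through.** **Inputs.** Appendix B gives coefficients of 0.957 for ln(creatinine), 0.378 for ln(bilirubin) and 1.120 for ln(INR), a constant of 0.643, and multiplication by 10. On rounding it says: "The MELD score derived from this calculation will be rounded to the tenth decimal place and then multiplied by 10". I read this as one decimal place, so the initial score is a whole number. On sodium: "For candidates with an initial MELD score greater than 11, the MELD score is then recalculated as follows", with sodium limited to 125–137. The laboratory values below are illustrations, not trial data. The plan states no figure on this point to reproduce.

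**1. Points from one term, before rounding and sodium**

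- Creatinine: 9.57 × ln(ratio). Four points need exp(4/9.57) = 1.52-fold (values from 1.0 to 4.0).
- Bilirubin: 3.78 × ln(ratio). Four points need exp(4/3.78) = 2.88-fold (values of 1.0 or more).
- INR: 11.2 × ln(ratio). Four points need exp(4/11.2) = 1.43-fold.

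**2. New starter, INR not involved**

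INR 1.3, sodium 137:

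- Creatinine 1.0, bilirubin 2.0: 0 + 0.262 + 0.294 + 0.643 = 1.199, rounded to 1.2, MELD 12.
- Creatinine 2.0, bilirubin 4.0: 0.663 + 0.524 + 0.294 + 0.643 = 2.124, rounded to 2.1, MELD 21.
- Change +9 (unrounded 13.35 × ln 2 = 9.25).

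Sodium alone, 137 to 132 at an initial score of 14: 1.32 × 5 − 0.033 × 14 × 5 = 6.60 − 2.31 = +4.29.

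Both exceed 4 points with INR unchanged. Both are discarded if an INR-affecting anticoagulant was started in between.

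**3. Prior user, INR only**

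Creatinine 1.0, bilirubin 2.0, INR 2.0 to 3.0:

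- INR 2.0: 0.262 + 0.776 + 0.643 = 1.681, MELD 17.
- INR 3.0: 0.262 + 1.230 + 0.643 = 2.135, MELD 21.
- Sodium 137: +4, meeting the definition (unrounded 11.2 × ln 1.5 = 4.54).
- Sodium 135: 17 becomes 17 + 2.64 − 1.122 = 18.52, and 21 becomes 21 + 2.64 − 1.386 = 22.25. Change +3.74, not an event. If the scores were left effectively unrounded, it would be 4.54 × 0.934 = 4.24.
- Sodium 130: 4 × 0.769 = 3.08, or 4.54 × 0.769 = 3.49 unrounded. Not an event either way.

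Smaller changes fall short even at sodium 137: INR 2.0 to 2.5 gives 2.5 points and 2.5 to 3.0 gives 2.0, both unrounded.

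**4. Why a held INR must be a named value**

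Creatinine 1.0, bilirubin 2.0, sodium 137 to 130:

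- INR held at 1.0: initial score 9, below the sodium step, change 0.
- INR held at 2.5: initial score 19, change 1.32 × 7 − 0.033 × 19 × 7 = 9.24 − 4.39 = +4.85.

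The same sodium change is or is not an event according to the INR chosen.

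**5. Number exposed**

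The documents do not give it. For scale only, 90% of 210 is 189. An assumed 3–10% on an anticoagulant would be about 6–19 subjects. That counts exposed subjects, not misclassified events.

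**The case against.** The strongest defence concerns prior users. Their MELD baseline is normally measured on the drug, so a stable drug effect cancels, whereas starting the drug later breaks the comparison. That is a sound reason to single out new starters. What remains is large fluctuation, which low sodium damps when both initial scores exceed 11, and a blinded medical review stands between a laboratory rise and an event. The main protocol may also have kept such subjects out. All of this stands, and it makes the second limb a gap of unknown size, not a demonstrated error. The gap does not close entirely even if users were barred at entry: with "The first valid MBT test will be defined as the baseline and day 0 of follow up", a subject who started the drug at week 10 and had a first valid test at week 24 is outside the rule. That requires there to be no valid screening test, although Protocol 10.1 schedules one.

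For new starters the defence is weaker. The review has no stated power to restore an event that the rule excludes. Exploratory analysis 14 drops MELD progression for everyone, so it shows sensitivity to the component but does not recover lost events.

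A reader might infer more than the documents support:

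- *That new starters are removed from the analysis.* They are not. They stay in the ITD and PP sets, their other components count, and a MELD rise before the start counts.
- *That ordinary INR swings in prior users become primary events.* Only large changes reach 4 points, and adjudication intervenes.
- *That the Conatus-defined secondary endpoint is equally affected.* SAP 8.4.2.5 takes events as defined and adjudicated under the main protocol, so the rule's application there is not established.

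**Conclusion.** The concern holds for new starters as a defect in the rule itself. Followed exactly, it discards any MELD progression after the anticoagulant start, including rises of 4 to 9 points to which INR contributed nothing, and leaves the subject at risk as event-free for that component. For prior users it holds as an omission: a 1.43-fold INR rise can by itself give 4 points at sodium 137 or above, and neither the SAP nor any stated review criterion says how to treat it.

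The point sizes follow from Appendix B under assumed laboratory values and one-decimal rounding. The number of subjects affected, and the size and direction of any effect on the hazard ratio, cannot be determined from the documents. The change is worth making because a more accurate rule is available from data that the present rule already needs.

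**What to change.** Replace the exclusion sentence in SAP 8.4.1 with:

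*For MELD assessments made while a subject is on a PT/INR-affecting anticoagulant started after the first valid MBT, MELD is calculated with INR held at the last value before the anticoagulant start; a rise of ≥ 4 points from baseline counts as progression.*

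For subjects already anticoagulated at the first valid MBT, keep the primary calculation unchanged and add two things:

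- a prespecified sensitivity analysis with INR held at the baseline-MELD value in both scores;
- an instruction to the blinded adjudicators to flag MELD rises that fall below 4 points when INR is so held.

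Holding INR for prior users belongs in a sensitivity analysis because in the primary analysis it would also drop genuine INR-driven deterioration.

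The cost is SAP wording and one extra derivation step, using laboratory values and anticoagulant dates that the present rule already requires. SAP section 2 allows amendment until the sponsor accesses the frozen or locked data. The remaining downside is that a genuine INR-driven rise in a new starter is still not counted, as under the present rule.

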10 STUDY PROCEDURES

10.1 *General*

The schedule of the breath tests is based on the schedule of the IDN-6556-17 protocol. The first MBT will be performed during the screening period (Week -4 to Day 0). The subsequent MBTs will be performed at 24 -week interval visits and at the final treatment visit, respectively.

10.2 *Breath Test Procedure*

Preparation of the study subject

Once consented, the patients will perform the breath test. In preparation for each breath test the patient will be asked to comply with the following precautions:

Exalenz Bioscience Ltd.	Last update: May 24, 2017
Study Title: Companion protocol for the ¹³ C-Methacetin Breath Test using the BreathID® MCS System for Conatus phase 2 study of Emricasan, an Oral Caspase Inhibitor, under protocol IDN-6556-17 (IND111463)	Protocol: CON-EX-0217 Version: 2.0
Document Nº: CSP000001	Page 24 of 28

1. Subject should be fasting, including all oral morning medications (except for beta-blockers and study drug [emricasan or placebo]), for at least 8 hours prior to the test
2. Subject should not smoke on the day of the breath test prior to the breath test
3. Subject should not take any of the following drugs within 48 hours prior to the test: acyclovir, allopurinol, carbamazepine, cimetidine, ciprofloxacin, daidzein (herbal), disulfiram, echinacea, enoxacin, famotidine, fluvoxamine, methoxsalen, mexiletine, montelukast, norfloxacin, phenylpropanolamine, phenytoin, propafenone, rifampin, terbinafine, ticlopidine, thiabendazole, verapamil, zileuton or any medication that might interfere with methacetin metabolism or might affect CYP1A2 (cytochrome P450 1A2)
4. Subject should not take amiodarone within 30 days prior to the test
5. Subject should not take paracetamol (acetaminophen) related medications within the 24 hours prior to the test
6. Subject should not perform the test if allergic or hypersensitive to Methacetin or its metabolites (paracetamol, acetaminophen)
7. Subject should not consume any alcohol or caffeine within 24 hours prior to the test
8. Subject should not have general anesthesia or sedation within 24 hours prior to the test
9. Subjects on beta-blockers or statins should be on a stable dose at least 30 days prior to the test

Preparation of ¹³C-Methacetin

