7 ANALYSIS SETS

7.1 *Safety Analysis Set*

The Safety analysis set will include all subjects (randomized and non-randomized into the Conatus emricasan study under protocol IDN-6556-17) that initiated at least one MBT (had taken Methacetin), even if the MBT was not completed or the result was not valid.

7.2 *Intent To Diagnose (ITD) Analysis Set*

The intent to diagnose (ITD) analysis set will include all subjects that were randomized into the Conatus emricasan study under protocol IDN-6556-17 and that had at least one valid MBT result.

7.3 *Per Protocol (PP) Analysis Set*

The per protocol (PP) analysis set will include all subjects from the ITD analysis set who did not have any major protocol deviations and exclude any subject that had a previous transjugular intrahepatic shunt (TIPS) or bariatric surgery that may affect the efficacy of the breath test.

Exalenz Bioscience Ltd.	Last update: August 8, 2019
SAP for Protocol CON-EX-0217: Companion protocol for the ¹³C-Methacetin Breath Test using the BreathID® MCS System for Conatus phase 2 study of Emricasan, an Oral Caspase Inhibitor, under protocol IDN-6556-17 (IND111463)	Document Version: 1.0
Document N°: CSD00109	Page 11 of 21

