8.3 Disposition of Patients

Subject dispositions will be summarized based on all subjects screened into the study, and for each treatment group.

The following subject disposition information will be presented:

- The number and percentage of subjects who had valid MBT for each visit.
- The number and percentage of reasons for not having a valid MBT for each visit.
- The number and percentages of subjects that were excluded from the PP analysis set, by reason for exclusion.

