8.4.2 Secondary Endpoints

8.4.2.1 The overall event-free survival with a second predefined cut-off

The event free survival will be analyzed in the same manner as the primary endpoint analysis with the exception that the dichotomous MBT result will be based on a second predefined cut-off: Any PDR_{peak} value of less or equal to 7.5 %/h (see **Appendix A** for detailed description of parameter calculation) will be considered as 'high risk' and any value above that threshold will be considered as 'lesser risk'.

Exalenz Bioscience Ltd.	Last update: August 8, 2019
SAP for Protocol CON-EX-0217: Companion protocol for the ¹³C-Methacetin Breath Test using the BreathID® MCS System for Conatus phase 2 study of Emricasan, an Oral Caspase Inhibitor, under protocol IDN-6556-17 (IND111463)	Document Version: 1.0
Document N°: CSD00109	Page 15 of 21

8.4.2.2 *The one-year event-free survival*

The one-year event free survival will be analyzed in the same manner as the primary endpoint analysis with the exception of censoring all subjects after 1 year (365 days) from baseline MBT date.

This analysis will be repeated while using the second pre-defined cut-off described in the first secondary endpoint (section 8.4.2.1).

8.4.2.3 *The event free survival when using all the repetitions of the MBT measurements (time dependent parameter)*

The event free survival will be analyzed in the same manner as the primary endpoint analysis with the exception of using all repetitions of the MBT measurements while dividing the prediction times to the intervals between tests by applying the Time dependent covariate method.

This analysis will be repeated while using the second pre-defined cut-off described in the first secondary endpoint (section 8.4.2.1).

8.4.2.4 *The six-month event-free survival*

The six-month event free survival will be analyzed in the same manner as the primary endpoint analysis with the exception of censoring all subjects after six months (180 days) from baseline MBT date.

This analysis will be repeated while using the second pre-defined cut-off described in the first secondary endpoint (section 8.4.2.1).

8.4.2.5 *The event-free survival considering only new hepatic decompensation events as defined in Conatus study protocol IDN-6556-17*

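### The SAP starts the survival clock at the screening MBT in 8.4.1 but at the first valid MBT in 8.2, so a late first valid test adds time in which no event can count

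*SAP*

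**What the plan says.** SAP 8.2, on survival models: "The first valid MBT test will be defined as the baseline and day 0 of follow up". The MELD baseline is then taken on or after that same test.

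SAP 8.4.1, on which events count: "the first of the hepatic decompensation events after the first valid MBT will be used". The same section then gives the time variable: "The time-to-first event will be derived as the number of days between the day of the screening MBT test" and the event or censoring date, with one day added.

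SAP 7.2 admits to the ITD set randomized subjects "that had at least one valid MBT result", at any visit. The PP set, which 7.4 makes the principal efficacy set, is drawn from ITD (7.3).

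The secondary analyses follow the primary one with changes. SAP 8.4.2.4 specifies "censoring all subjects after six months (180 days) from baseline MBT date", and 8.4.2.2 does the same at 365 days. SAP 8.4.2.3 uses all MBT measurements, "dividing the prediction times to the intervals between tests by applying the Time dependent covariate method".

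**The concern.** Both rules stand in the SAP, so its clause that the SAP prevails over the protocol cannot choose between them. Two programmers, one following 8.2 and the other the explicit formula in 8.4.1, would derive different times for the same subject in the primary analysis.

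If the formula is followed, a subject whose screening test was invalid carries time before the first valid test. That time is event-free by construction and is credited to an MBT class not yet measured. This immortal time can bias the hazard ratio and lowers the Kaplan-Meier event rates.

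The one-year, time-dependent and six-month analyses are steps in the testing hierarchy of SAP 6.2, so the ambiguity reaches formal tests beyond the primary one.

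**Working it through.** The documents give no event count, hazard ratio or power for the primary analysis, so there is no planned figure to reproduce.

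**1. Anchors side by side**

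| Item | Anchor | SAP section |
|---|---|---|
| Day 0 for survival models | First valid MBT | 8.2 |
| MELD baseline | On or after first valid MBT | 8.2 |
| Qualifying events | After first valid MBT | 8.4.1 |
| Anticoagulant exclusion for MELD progression | After first valid MBT | 8.4.1 |
| Time to event | Screening MBT | 8.4.1 |
| 180- and 365-day windows | Baseline MBT date | 8.4.2.4, 8.4.2.2 |

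Only the time variable names the screening test.

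**2. Can the dates differ?** Yes. No section requires a valid screening test. Appendix A sets validity conditions, and SAP 8.3 will tabulate "The number and percentage of reasons for not having a valid MBT for each visit".

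**3. Dates.** Protocol 10.1 places the first MBT between week -4 and day 0, and later tests at 24-week intervals.
- First valid test at week 24: 24 × 7 = 168 days, plus 0 to 28 days of screening = 168 to 196 days added.
- First valid test at week 48: 336 + (0 to 28) = 336 to 364 days added.
- No screening MBT: the formula has no start date.

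**4. Six-month window for a week-24 starter on the screening clock**
- Window counted from the first valid MBT: follow-up ends at 168 + 180 = 348 to 196 + 180 = 376 days on the clock.
- Window counted from screening: at most 180 − 168 = 12 at-risk days remain, and none if the gap is 180 days or more.

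**5. Simulated effect on the HR.** N = 0.90 × 210 = 189, from SAP 4.1. All other inputs are assumptions: true HR 2.0, 40% high risk, 35% overall one-year event risk, exponential event times from the first valid MBT, a gap of 168 to 196 days for late subjects, and follow-up of 350 to 700 days from screening. A Cox model with the binary MBT class was fitted in 2,000 runs per setting. HR on the screening clock:

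| Late share | Late subjects 40% high risk (equal mix) | 60% high risk | 25% high risk |
|---|---|---|---|
| 5% | 2.01 | 1.95 | 2.03 |
| 10% | 1.98 | 1.92 | 2.08 |
| 20% | 1.99 | 1.82 | 2.12 |

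The standard error of log HR is about 0.22 (81 to 85 events). The largest shift is ln(2.00/1.82) = 0.094, and 0.094/0.22 = 0.43 standard errors. Repeat runs of 3,000 agree within 0.04 in HR. In the 60% column at 20% late, power falls from 87% to 77%; at 10% late it falls by about 4 to 5 points.

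**6. Kaplan-Meier event share at day 365, equal mix**

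| MBT class | Correct clock | 5% late | 20% late |
|---|---|---|---|
| High risk | 46.8% | 45.8% | 42.8% |
| Lesser risk | 27.0% | 26.4% | 24.6% |

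**7. Six-month analysis, 20% late**
- Window from the first valid MBT, clock from screening: HR 1.97 with equal mix, and 1.65 or 2.27 with unequal mix, against 2.00 to 2.02 with one origin. The event count is unchanged.
- Window and clock both from screening, equal mix: events fall from 36.7 to 29.5, a loss of 7.2/36.7 = 20%.

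**8. A second simulation** (400 runs; 35% one-year risk in the lesser-risk group) points the same way. With 5% to 30% late in both classes, the screening-clock HR is 1.98 to 1.99. With 30% of high-risk and 10% of lesser-risk subjects late, it is 1.77 against 2.01 on the correct clock, and 2.22 against 2.00 with the shares reversed. The first of these is ln(2.01/1.77) = 0.127, or about 0.6 of a standard error of 0.22. Starting the clock at the first valid MBT, or keeping the screening clock with delayed entry at that test, gives 1.99 to 2.02 throughout.

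**The case against.** The rules may diverge for few subjects. If the screening test is the first valid one, they agree apart from the added day, which shifts everyone equally and leaves Cox and log-rank results unchanged. A test aborted for vomiting is repeated the next day (Protocol 10.2), and the Appendix A validity conditions are not demanding. A subject with no screening test gains no time, because the formula cannot be computed. The extra days therefore need a screening test that was attempted, was invalid, and was not validly repeated before week 24. Nothing in the documents supports 10% or 20% of such cases.

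Bias in the HR also requires late first tests to differ by MBT class, which no section suggests. The remark in SAP 8.4.3.2 that missing values were unrelated to outcome concerns the MBT-change endpoint; if it held here too, the unbiased case would be more likely. PP exclusions, possibly including an invalid screening test as a major deviation (a term the SAP does not define), would reduce N and make any shift smaller relative to noise. Section 8.2 arguably defines the baseline MBT date already. Usual start-stop coding of 8.4.2.3 would drop an interval with no MBT value, which amounts to delayed entry and is unbiased.

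Most of this stands as a limit on size, and the 10% and 20% rows are illustrations only. It does not remove the conflict: the SAP gives an explicit formula that contradicts its own baseline rule, and the less favourable readings of the secondary windows remain open.

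**Conclusion.** The concern holds. The contradiction is in the current SAP text and affects the derivation of the primary time variable. Followed literally, 8.4.1 gives a wrong time for any subject with an invalid screening test and a later first valid test, and no time for a subject never tested at screening.

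Confidence is high in the conflict and low in its numerical effect, because the number of late first tests is not stated. Under the main simulation's assumptions, the primary HR is essentially unbiased if late tests are balanced across MBT classes and moves by less than half a standard error, in either direction, if they are not; only the more extreme imbalance in the second simulation goes beyond that. Kaplan-Meier estimates are lowered in both cases. The six-month analysis is the most exposed: with mixed origins its HR moves further than the primary one, and with a screening origin it loses events. This should be corrected, but it does not by itself undermine the primary analysis.

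**What to change.** - In SAP 8.4.1, replace the screening MBT date with the first valid MBT date, in both the sentence and the formula. This applies the rule already in 8.2.
- State that the baseline MBT date in 8.4.2.2 and 8.4.2.4 is that same date, and that the first interval in 8.4.2.3 starts there.
- Use one day-count convention; 8.2 calls the origin day 0, while the formula makes it day 1.
- Report how many subjects had their first valid MBT after the first dose of study drug. A sensitivity analysis without them is optional.

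The cost is one corrected sentence, one clarifying phrase in each of two secondary endpoints, a start point for 8.4.2.3 and one programmed variable. No new data are needed. SAP section 2 requires amendments before the sponsor accesses the data; after that, the derivation actually used should be documented in the clinical study report.
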